HYPOTHESIS 3. Participants randomly assigned to the intervention arm will demonstrate an increase in physical activity at 9- weeks as measured by medium to large effect sizes, and this increase in positive affect/reduction in negative affect will be mediated by an increase in physical activity.

AIM 4. We will explore the relationship between physical activity and the brain between groups at baseline and 9-weeks, in order to determine whether an improvement in brain network connectivity and function is associated with an increase in physical activity.

HYPOTHESIS 4. Participants randomly assigned to the intervention arm will demonstrate an increase in physical activity and brain network connectivity and function at 9-weeks.

B. Background and Significance

Affective well-being is typically characterized as the presence of positive feelings and the absence of negative feelings over time, and have been showing to be relatively independent constructs (Lucas et al., 1996). After the age of 60, negative affect tends to remain stable, (Gross et al., 1997) but positive affect decreases (Kunzmann et al., 2000). Positive affect in late life has been positively associated with social engagement (e.g., Kunzmann, 2008), while negative affect in late life has been linked to self-reported physical health (e.g., Brief et al., 1993). Studies have demonstrated that exercise is associated with higher positive affect and lower negative affect (Dua et al., 1992; Rizk et al., 2015) In clinical samples, exercise has long been established as an

[figure not shown]

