effective treatment for depression in younger [Krogh et al., 2011] and older adults [Blake et al., 2009]. Importantly, exercise also addresses vascular risk factors thought to be particularly relevant to aging (Blaha et al., 2016), in general, as well as depression in late life [Alexopoulos et al., 2006, Sheline et al., 2010]. While there have been several studies demonstrating the benefits of exercise on depression in older adults, no known study has examined the positive benefits of a structured, group exercise program on mood and well-being in an aging sample. As an ancillary aim, we will also examine the impact of a structured exercise intervention on cognitive functioning. Fit and Strong!, a physical activity / behavior change program for older adults with lower extremity osteoarthritis, has demonstrated efficacy, effectiveness, and ease of dissemination for individuals with osteoarthritis living in the community [Hughes et al., 2004, 2006, 2010]. The goal of this study is to adapt Fit & Strong! for increasing positive affect and reducing negative affect and depressive symptoms among older adults residing in the community.

C. Research Design and Methods

C.1 General study design

We will enroll 40 subjects in this study between the ages of 60 and older, from the community who score at least 1 on the Patient Health Questionnaire-8 (PHQ). Up to 20 participants will have PHQ-8 scores of 1-4, while up to one-half of participants will have PHQ scores >4. At the outset of the study, up to 20 individuals will be randomly assigned to the intervention portion of the study, while up to 20 individuals will be randomly assigned to a crossover wait-list group, who will undergo the intervention beginning at study week 10. Outcome measures will be administered to all participants before the intervention and to the intervention group after they undergo the intervention. The wait-list group will complete all of their outcome measures before they begin the intervention(see Figure 1).

Figure 1

C.2 Phone screen and Study Visits

C2.1 Pre-Study Screen:

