Before being scheduled to a study visit, potential participants will undergo a phone or in-person screen where the aims and structure of the study will be explained to them. The potential participants will be allowed to ask specifics about the study and express their interest in the study. If they wish to participate in the study, they will undergo a phone screen assessing past and current medical and psychiatric history, as well as answer a six-item screener, Patient Health Questionnaire-8 and Physical Readiness Questionnaire. Participants will also be informed about compensation during the phone screen. If a participant scores 10 or higher on the PHQ, but refuses to participate in the study, we will refer them to a list of treatment facilities including UIC's Psychiatry Outpatient Program. Scores above 10 or 11 are thought to be indicative of clinical depression (see <https://www.ncbi.nlm.nih.gov/pubmed/18752852> or <https://www.ncbi.nlm.nih.gov/pmc/articles/PMC2943487/>) Participants who express interest and are eligible for the intervention group will also be screened with the MRI Screening document to see if they are eligible for the optional MRI component of the study.

C2.2. Study Enrollment and Pre-Intervention Measures (approximately 3 hours)

All eligible individuals will be invited to the University of Illinois at Chicago or to Oakwood Shores for their first study visit, which will last approximately two hours. First, the entire study will be described to participants and any questions that they have about the study will be answered. After the participant has signed the consent form, they will participate in an interview with a trained research assistant. Some of these questions will be of a personal nature and may make the participant feel uncomfortable. They can decline to answer any question. Next, they will complete a packet of self-report questionnaires and will undergo a neuropsychological (memory/cognitive) testing battery and mobility assessment with a trained staff person. Randomized participants of the intervention group will be invited to participate in optional MRI testing which will take place pre-intervention (Week 0) and post-intervention (Week 9).

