Inclusion Criteria for All Participants: a) ages 60+; b) Sufficient visual and hearing capacity to follow instructions; c) a score of at least 1 on the Patient Health Questionnaire-8 (Kroenke et al., 2001); d) Six Item Screener (Callahan, 2002) score > 4; e) pass screening with the EASY scale [Cardinal et al., 1996] or have doctor's clearance to participate; e) no recent (<6 months) joint replacements; f) physically inactive (<150 minutes of exercise per week); and g) able to walk at least 20 feet (with or without the aid of a cane or walker); speak English proficiently. *In the event we need a doctor's clearance for a subject to participate, we would have the participant sign a release of information for us to contact their doctor and then we would contact the doctor via pager/phone and get verbal permission to allow them to participate in an exercise study. They would then sign a form to document their authorization.

C.4.2 Exclusion Criteria:

a) Non-proficient in English; b) 0 on the Patient Health Questionnaire-8 (Kroenke et al., 2001); cb) Six Item Screener < 5 (Callahan, 2005); c) fail screening with the EASY scale and does not have doctor's clearance to participate; d) joint replacement in last 6 months; e) 150+ minutes of exercise per week; g) unable to walk at least 20 feet; f) severe medical illness (i.e., metastatic cancer, brain tumors, unstable cardiac, hepatic, or renal disease, myocardial infarction or stroke) within the 3 months preceding the study; g) Other brain/neurological disorders (i.e., dementia or delirium according to DSM-IV criteria, history of severe head trauma, Parkinson's disease or Parkinson's plus syndromes, multiple sclerosis, epilepsy); h) Conditions often associated with depression (i.e., endocrinopathies other than diabetes, lymphoma, and pancreatic cancer).

Potential participants for the optional MRI study will be excluded for the following: a) cardiac pacemaker or defibrillator: b) metal parts in head, spinal cord, eyes, or chest: d) past operation or radiation therapy with skull or brain: e) aneurysm clips: f) dentures that have been surgically implanted with magnets, braces: g) claustrophobia: h) heart valve replacement: i) history of work with metal resulting in an injury: j) eye injury with metal: k) history of strokes/seizures: l) participants in the waitlist group.

C.5 Recruitment and Attrition Considerations

C.5.1 Recruitment:

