machine will produce imaging of each participant's brain. Participants will be allowed to request earplugs to wear during the procedure, as the machine is quite noisy. In the case that a participant should start to feel claustrophobic, the MRI testing will be stopped immediately. The total time each participant will be asked to stay inside the machine should be no more than an hour. MRI testing will take place at baseline before the exercise intervention and after the intervention (week 9). A taxi will be provided to and from the imaging center for participants that need it. Participants will be paid \$50 at each session (\$100 total).

C 6.7. Data Analysis/Interpretation: Participation rates and program acceptability ratings will be quantified. Changes in depressive symptoms and positive and negative affect will be analyzed using a repeated measures ANOVA model. Between-group analyses will be conducted to determine whether significant changes occur in the outcomes between baseline, 9- and 18-weeks to examine maintenance effects over time. A mixed-effects model will be used to determine whether intervention participants significantly increased their participation in physical activity between baseline and 9- and 18-weeks. Within-group analyses will also be conducted to determine whether participants improved in depressive symptoms, positive and negative affect, and physical activity between baseline, immediately following Fit & Strong! participation, and 2 months post-Fit & Strong! participation. Finally, the Baron and Kenny Causal Steps approach [Baron and Kenny, 1986] will be used to determine whether change in physical activity between baseline and immediately post Fit & Strong! mediates the decrease in depressive and positive and negative affect. A process evaluation will be conducted to measure aspects of program implementation including fidelity, intervention dose received, participant attrition, and program acceptability ratings. [Washburn et al., 1993; Miller et al., 1992; Bellamy, 1989; Hughes et al., 1991; Resnick and Jenkins, 2000] See Appendix C. [Maust et al., 2013; van Loon et al., 2013]

C 6.8. Data and Safety Monitoring Plan

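### Aim 4 promises a between-group imaging comparison, but wait-list participants are excluded from MRI, so the comparison has no control data

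*Combined protocol and SAP*

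**What the plan says.** - **Section A, Aim 4:** "We will explore the relationship between physical activity and the brain between groups at baseline and 9-weeks". The stated purpose is to see whether better brain network connectivity and function goes with more physical activity.
- **Section A, Hypothesis 4:** "Participants randomly assigned to the intervention arm will demonstrate an increase in physical activity and brain network connectivity and function at 9-weeks". It names no comparator.
- **C.1, arm size:** "up to 20 individuals will be randomly assigned to the intervention portion of the study", with the same ceiling of 20 for the crossover wait-list arm.
- **C.1, wait-list measurement:** "The wait-list group will complete all of their outcome measures before they begin the intervention".
- **C2.2:** "Randomized participants of the intervention group will be invited to participate in optional MRI testing", at weeks 0 and 9. C2.1 likewise ties the MRI screening form to people eligible for the intervention group.
- **C.4.2, MRI exclusions, last item:** "l) participants in the waitlist group".
- **C.6.6:** describes two scanning sessions, before and after the intervention, without naming an arm.
- **C 6.7:** gives methods for affect and mood ("Changes in depressive symptoms and positive and negative affect will be analyzed using a repeated measures ANOVA model"), for physical activity and for mediation. It does not mention imaging.

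**The concern.** The aim sets up a comparison that the eligibility rules prevent. A reader of Aim 4 would expect imaging in both randomized arms. The protocol supplies it in one.

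Without wait-list scans, a week 0 to week 9 imaging change in the intervention arm cannot be separated from the passage of time or the effect of repeat scanning. Self-selection into an optional scan adds a further limit, mainly on whom the result applies to. Because C 6.7 specifies no imaging analysis, nothing in the plan prevents an uncontrolled pre-post change from being reported as an effect of the exercise program.

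**Working it through.** The documents give no sample size, power or effect size for imaging, so there is no stated figure to reproduce. The check is structural.

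**1. Fill the arm-by-time imaging cells.**

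| Arm | Week 0 scans | Week 9 scans | Source |
|---|---|---|---|
| Intervention | at most 20 | at most 20 | C.1 ceiling; C2.2 invitation |
| Wait-list | 0 | 0 | C.4.2, item l |

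Two of four cells are empty. At the enrolment ceilings, a full two-arm comparison would use (20 + 20) × 2 = 80 scans. At most 20 × 2 = 40 can exist, all in one arm.

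**2. Standard error of a between-arm difference.** SE = SD × √(1/n₁ + 1/n₀). With n₀ = 0 it is undefined, whatever the value of n₁.

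**3. Rank of the model.** A model with intercept, group, time and group × time has four columns. With scans in the intervention arm only, the design matrix has rank 2 of 4: group is aliased with the intercept, and group × time with time. With both arms scanned the rank is 4 of 4. A between-arm difference in the activity-brain slope fails for the same reason, since there is no wait-list slope.

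**4. How many could be scanned.** The ceiling of 20 assumes that every intervention participant is MRI-eligible, accepts and completes. C.5.2 expects 33% not to complete: 20 × 0.67 = 13.4, so about 13 with both scans. MRI exclusions and refusals would lower this further; the documents give no rate for either.

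**5. Precision of what remains.** For a within-arm correlation, Fisher's z has SE = 1/√(n − 3). An observed r of 0.5 is taken for illustration, with atanh(0.5) = 0.549.
- n = 20: SE = 1/√17 = 0.243; 0.549 ± 1.96 × 0.243, back-transformed, gives a 95% CI of 0.07 to 0.77.
- n = 13: SE = 1/√10 = 0.316; 0.549 ± 1.96 × 0.316, back-transformed, gives a 95% CI of −0.07 to 0.82.

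The smallest correlation detectable with 80% power at two-sided alpha 0.05 (assumed) is tanh[(1.96 + 0.84) × SE]: about 0.59 at n = 20 and 0.71 at n = 13. The single-arm associations can be estimated, but imprecisely.

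**The case against.** The strongest reply is that little is lost. The aim only sets out to explore, and MRI is an optional part of a pilot-funded study. The aim's purpose clause asks about an association that needs no control arm, and Hypothesis 4 claims nothing about the wait-list. Aim 3 uses almost the same phrase, so the wording may have been carried over, although the documents do not say so. All of this limits the weight of the point. None of it supplies wait-list scans.

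Three readings that might rescue the comparison do not succeed:

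- **The wait-list completes all its outcome measures (C.1).** This general sentence does not override a specific exclusion. The same applies to C.6.6 and to the consent section (D.2.1), which speaks of participants in general when it describes the MRI addendum.
- **The groups are PHQ-8 strata within the intervention arm.** The aims do not support this: Hypothesis 2 compares with wait-list participants, and Hypothesis 4 speaks of the intervention arm.
- **The general between-group analyses in C 6.7 cover imaging.** The outcomes named there are depressive symptoms, affect and physical activity. If imaging were included, the plan would prescribe an analysis with no control data.

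It is also fair to say that the missing imaging analysis in C 6.7 is a separate omission, which would remain after Aim 4 was reworded. It matters here because no alternative analysis is specified to take the place of the impossible one.

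**Conclusion.** The concern holds. As written, Aim 4 contradicts the MRI eligibility rule. The decisive figure is zero wait-list scans at both time points, which follows from the text and rests on no assumed number. The ceiling of 20 per time point and the figure of about 13 completers only describe how much single-arm information could exist.

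The scope is narrow. The imaging change in scanned intervention participants, its association with change in physical activity, and the activity-brain association at each time point can all be estimated, without a control. The between-arm comparison of physical activity itself is intact. The point should be fixed because a stated aim has no data on one side, but it is confined to an optional, exploratory component.

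**What to change.** 1. Delete the between-group wording from the imaging part of Aim 4.
2. Restate that part, and for clarity the imaging part of Hypothesis 4, as an exploratory single-arm analysis in intervention participants who accept MRI. State that imaging change will not be attributed to the intervention.
3. Add to C 6.7 the paired week 0 to week 9 imaging change, its association with change in physical activity, and the activity-brain association at week 0 and at week 9. Report each with a 95% confidence interval and the number scanned at each time. Name the imaging measure or measures to be used, since C.6.6 names none and the paired change is otherwise undefined.

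The cost is wording in section A and a short paragraph in C 6.7, with no added scans, participants or visits. The price is a weaker imaging claim.

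Keeping the between-group comparison would instead mean removing the wait-list exclusion and adding up to 20 × 2 = 40 wait-list scans. At the plan's $100 per person for two scans (C.3, C.6.6), participant payments would be up to 20 × $100 = $2,000, plus scanner costs that the documents do not give. Precision would still be limited: at 20 per arm the SE of a between-arm difference is √(1/20 + 1/20) = 0.32 SD, and at 13 per arm it is 0.39 SD. That option is not proposed.

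### Participants are banded by PHQ-8 at entry, but no stratification by band is stated and the planned ANOVA has no band or baseline-severity term, so chance imbalance goes uncontrolled

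*Combined protocol and SAP*

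**What the plan says.** Section C.1 sets the total: "We will enroll 40 subjects in this study between the ages of 60 and older". It then sets the severity mix: "Up to 20 participants will have PHQ-8 scores of 1-4, while up to one-half of participants will have PHQ scores >4". Section C.4.1 requires "a score of at least 1 on the Patient Health Questionnaire-8", and section C.4.2 excludes people who score "0 on the Patient Health Questionnaire-8". The two bands therefore cover every eligible person and do not overlap.

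On allocation, C.1 says that "up to 20 individuals will be randomly assigned to the intervention portion of the study" and that "up to 20 individuals will be randomly assigned to a crossover wait-list group". It names no stratum, block or minimisation factor. Figure 1, to which it refers, is not available in the text.

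On analysis, C 6.7 says: "Changes in depressive symptoms and positive and negative affect will be analyzed using a repeated measures ANOVA model". It adds a mixed-effects model for physical activity, within-group comparisons and a causal-steps mediation analysis. None of these names PHQ-8 band or baseline severity as a factor or covariate.

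The PHQ-8 appears under C.6.1 as a screening measure. C.6.3 includes depression and affect in its summary of outcomes, but it describes no depressive-symptom scale.

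**The concern.** The protocol controls the severity mix at enrolment and then, as far as the text shows, makes no further use of it. Severity at entry is a natural candidate for predicting how far a symptom score will move. A person near the floor has little room to fall, whereas a person with a higher score has more room and is also more subject to regression to the mean. If one arm happens to receive more high-band participants, part of any difference in change between arms can come from that mix and not from the programme.

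At stake are the precision and interpretability of the Aim 2 comparison. The arms are small, and C.5.2 expects 33% of participants not to complete. The band is known from screening (C2.1), so the information needed to prevent this is already collected.

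**Working it through.** **Inputs from the documents.** Total 40; arms of up to 20 each; low band (PHQ-8 1-4) up to 20; high band (>4) up to one-half of participants (all C.1); entry score at least 1 (C.4.1); 33% non-completion (C.5.2). The documents give no band means, SDs or numerical effect size.

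**1. The total of 40.** The low band is at most 20 and the high band at most half of 40, which is 20. The only pair that sums to 40 is 20 + 20, so the stated total is reproduced, but at one point only. If one-half means half of those actually enrolled, the high band can never exceed the low band. With 15 in the low band the ceiling is then 15 + 15 = 30, against 15 + 20 = 35 under a fixed limit of 20.

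**2. Room to fall on the PHQ-8.** With a floor of 0, a low-band participant can fall by 1 to 4 points at most. Every high-band participant has room for at least 5.

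**3. Chance imbalance without strata.** Let X be the number of high-band participants in one arm of 20, drawn from 40 of whom 20 are high-band. Then P(X = k) = C(20,k)² / C(40,20).

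- P(X = 10) = 0.2476, P(X = 11) = P(X = 9) = 0.2047, P(X = 12) = P(X = 8) = 0.1151.
- 12:8 or worse: 1 − 0.2476 − 2 × 0.2047 = 0.343.
- 13:7 or worse: 0.343 − 2 × 0.1151 = 0.113.
- 14:6 or worse: 0.026.

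Randomising within band would hold the split at 10:10.

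**4. What a 12:8 split does to baseline (illustration on assumed values).** The shares of high-band participants are 0.6 and 0.4, a difference of 0.2. Assume band means of 2.5 and 9 and within-band SDs of 1.1 and 3.5.

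- Baseline gap: 0.2 × (9 − 2.5) = 1.3 points.
- Total SD: √[0.5 × (1.1² + 3.5²) + 3.25²] = 4.16, so the gap is 1.3 / 4.16 = 0.31 SD.
- With a high-band mean of 7 to 11, the gap runs from 0.2 × 4.5 = 0.9 to 0.2 × 8.5 = 1.7 points.

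**5. What it does to the planned contrast.** With two time points, the group-by-time test in a repeated measures ANOVA compares mean change between arms. A stable difference in level between bands cancels. What remains is 0.2 × (difference between bands in mean change). Suppose that scores in both arms drift down by a fraction r of baseline, whatever the treatment. The distortion is then 1.3 × r.

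- r = 0.10: 0.13 points, or 0.13 / 4.16 = 0.03 SD.
- r = 0.30: 0.39 points, or 0.39 / 4.16 = 0.09 SD.
- Over the 0.9 to 1.7 point range of gaps: from 0.9 × 0.10 = 0.09 to 1.7 × 0.30 = 0.51 points.

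If the benefit of the programme itself differs by band, that comes on top. The documents give nothing from which to size it.

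**6. After loss.** 40 × 0.67 = 26.8, so about 27 complete: about 13 per arm and 6 or 7 per band per arm. Balance at randomisation does not guarantee balance among completers, which is a reason to adjust in the model as well as stratify.

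**The case against.** The strongest reply is that unstratified randomisation is valid. A 0.31 SD gap is about one standard error of a baseline difference with 20 per arm (√(2/20) = 0.316 SD). Any covariate reaches that in about a third of trials, and standard errors already allow for it. The analysis also uses each person's own baseline. The PHQ-8 is only a screener here, so the floor argument does not automatically carry over to the depressive-symptom outcome, still less to positive and negative affect. And this is a feasibility pilot with no stated power calculation. All of that stands, and it limits the point to precision and chance imbalance.

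It does not remove the point. A change-score comparison does not adjust for change that depends on baseline, whereas a covariate would, at almost no cost.

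The documents do not support four stronger readings that a reader might infer:

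- *The 0.31 SD gap is the error in the treatment effect.* It is a baseline gap on assumed values. The distortion of the change contrast in the illustration is 0.03 to 0.09 SD.
- *The between-band spread in level inflates the error of the group-by-time test.* Stable level differences fall into between-subject variance. Only differences in change matter.
- *The investigators decided to ignore band when allocating.* The text is silent on method, so one can say only that no stratification is stated.
- *The limits will leave the trial short of 40.* A full band can be closed while the other keeps recruiting. Nothing in the documents shows that one band will fail to fill, and relaxing the limits would trade away some of the intended severity mix.

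**Conclusion.** The point holds as one of precision and chance imbalance. No stratification by PHQ-8 band is stated, and the planned ANOVA carries no band or baseline-severity term. If both bands fill to 20 and the arms are 20:20, a split of 12:8 or worse occurs in about 34% of unstratified allocations and 13:7 or worse in about 11%. Those figures need only the counts in C.1.

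The consequence for the efficacy contrast rests on assumptions: that change depends on baseline severity, and that this carries over from the PHQ-8 to the scales actually analysed. In the illustration it is a few tenths of a point on a PHQ-8-like scale, well below the 1.3-point baseline gap. This is not systematic bias and does not invalidate the design. The change is worth making because it is cheap and the band is already known at screening. The wording of the two limits is a secondary matter of clarity.

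**What to change.** - In C.1, state the allocation method and randomise within PHQ-8 band (1-4 and >4).
- In C 6.7, analyse each 9-week outcome with the baseline value of that outcome and PHQ-8 band as covariates, by ANCOVA or an equivalent mixed model.
- In C.1, say whether the two limits are firm quotas or a target split, whether one-half refers to 40 or to those enrolled, and what happens if one band fills first. Firm quotas protect the severity mix but make 40 depend on both bands filling. A target split makes 40 easier to reach but may give a less even mix.

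The cost is a second randomisation list and one or two degrees of freedom in the model. No new data are needed for the band, and both bands stay in the trial.

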The clinician, [name] MD, PhD; Associate Professor; Associate Director, Residency Training and Education; Co-Director, Adult/Neuroscience Research Track; Department of Psychiatry, or research staff may remove a subject from the study if the clinical team thinks that the subject is at imminent suicidal risk, which, while not specifically assessed, may come up during the course of the study, given that individuals with significant depressive symptoms will be enrolled in the study. If the patient is deemed to have specific suicidal ideation during any of the visits, the PI and clinician will be immediately notified, and an appropriate clinical decision for emergent psychiatric evaluation will be made, including an evaluation of the need for hospitalization.. If the potential participant brings up suicidal ideation during the phone screen, they will be referred to the suicide prevention hotline.

D.2.1 Informed Consent

In most cases, potential subjects will learn basic information about the study during a telephone or in-person screening, and an informed consent will be mailed to those who are eligible for/interested in the study. At the time of initial contact with the study coordinator, subjects will be given detailed information about the study and the informed consent form will be reviewed and signed. Written consent from the participant will be obtained before the diagnostic interview begins. A copy of the document will be given to the study participant and the original informed consent document will be kept in a locked cabinet in the principal investigator's laboratory, separate from all other study materials. Other study materials (e.g., assessment measures) will be coded by an anonymous identification number. This identification number will be linked to the subject's name in an electronic database that can be accessed only by double password authentication. Participants will also be presented with an Informed Consent Addendum form addressing the MRI inclusion to the research study. They will be asked if they are willing to participate and will be informed of the additional compensation upon completion of each MRI

session. Participants will also be informed that refusal to participate in the MRI testing will have no effect on their participation in the research study.

D.3 Protections Against Risk

D.3.1 Protection Against Risk of Psychological and Social Discomfort

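### C2.1 ties the treatment-facility list to a PHQ score of 10 or higher plus refusal, and no visible text gives a score-based referral to people with that score who enrol or prove ineligible

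*Combined protocol and SAP*

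**What the plan says.** C2.1 (Pre-Study Screen) administers the PHQ-8 by phone or in person, before any study visit. It then sets a referral rule: "If a participant scores 10 or higher on the PHQ, but refuses to participate in the study, we will refer them". What the person receives is a treatment-facility list, which includes the university's own psychiatry outpatient service. The next sentence gives the reason for a threshold in this region: "Scores above 10 or 11 are thought to be indicative of clinical depression".

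The entry rules point the other way for people who accept. C.4.1 asks for "a score of at least 1 on the Patient Health Questionnaire-8", and the only PHQ-8 score excluded in C.4.2 is 0. C.1 plans that "up to one-half of participants will have PHQ scores >4", and randomises up to 20 people to a wait-list group "who will undergo the intervention beginning at study week 10". D.2.1 (Suicidal Risk) expects such people in the trial, "given that individuals with significant depressive symptoms will be enrolled in the study".

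For enrolees the visible safeguards are these:

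- **D.2.1 (Suicidal Risk):** "If the patient is deemed to have specific suicidal ideation during any of the visits, the PI and clinician will be immediately notified", with a decision on emergency psychiatric evaluation. Imminent suicidal risk can lead to removal from the study. The section describes that risk as something "which, while not specifically assessed, may come up during the course of the study".
- **D.3.1:** staff must act if someone is found to be a danger to self or others, and the PI is available during visits.
- **C 6.8 and D.1.3:** adverse events are evaluated, treated or referred, and followed up.

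**The concern.** The plan itself treats a score of 10 or higher as sufficient reason to point a person towards treatment, but it writes the offer only for a person who also declines. Two people with the same score at the same phone call are handled differently: one declines and is written in to receive the list, while the other agrees, may be told to wait until week 10, and is not. A third person, who is willing but turned away on another criterion, has not refused and so does not meet the condition either.

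What is at stake is patient safety on a small scale. A person above the plan's own depression threshold could pass through screening and, if enrolled, through the waiting period without being handed information that the study team already holds.

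**Working it through.** There is no planned figure to reproduce. The check is a reading of the referral rule against the entry and safety sections, with one short piece of arithmetic on the number of people.

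**Who meets the C2.1 condition?** The condition has two parts joined together: a score of 10 or higher, and refusal.

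| Person scoring 10 or higher | Can this happen under the plan? | Meets the C2.1 condition? | Any other referral triggered by the score? |
|---|---|---|---|
| Declines the study | Yes (C2.1) | Yes | Not needed |
| Enrols, intervention arm | Yes: floor of 1, no ceiling (C.4.1, C.4.2) | No, did not refuse | None visible |
| Enrols, wait-list | Yes: same entry rules; start at week 10 (C.1) | No, did not refuse | None visible |
| Willing but ineligible, for example exercising 150 minutes or more a week (C.4.2) | Yes | No, did not refuse | None visible |

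**Do the other safeguards reach these people?** Each one has its own trigger:

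- D.2.1 acts on suicidal ideation that comes to light at a visit, or on imminent risk. A potential participant who raises ideation during the phone screen is referred to a prevention hotline.
- D.3.1 acts on danger to self or others found during a visit.
- C 6.8 and D.1.3 act on adverse events. Neither section classes a high screening score as an adverse event.

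A person with a score of 10 or more who voices no ideation, poses no evident danger and has no adverse event falls outside all of them. D.1.5 mentions questions about a history of suicidal or homicidal behaviour, so ideation may surface more often than D.2.1 suggests. That is still a different trigger from the score.

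**How many enrolees could be affected?** The inputs, all from C.1, are 40 enrolled, up to 20 with scores of 1 to 4, and up to one-half with scores above 4.

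- Minimum above 4 at full enrolment: 40 − 20 = 20.
- Maximum above 4: 0.5 × 40 = 20.
- So exactly 20 people score above 4 if the trial fills.
- Those at 10 or higher are a subset of these 20, so their number lies between 0 and 20.

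The documents do not say where in that range it will fall, how many of these people would be on the wait-list, or how many willing but ineligible people will score 10 or higher.

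**The case against.** The strongest reply has three parts.

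First, C2.1 does not use the word only. It says what happens to people who refuse and is silent about everyone else. A reader might infer that enrolees are denied the list, and the documents do not say that. What stands is narrower: refusal is an explicit part of the condition, and no other visible section supplies a score-based referral.

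Second, the consent pages are not in the text available. D.3.1 shows that participant-facing safety information is placed in the consent document, so a list for enrolees could be there. This part of the reply stands, and the point must be conditional on it for enrolees. It helps less with people who are willing but ineligible, because D.2.1 (Informed Consent) describes mailing the form to eligible or interested people, and an ineligible person may never see it.

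Third, refusers and enrolees are not in the same position. Refusers leave contact with the study, and a list is all it can offer them. Enrolees have a psychiatry clinician, an available PI and regular staff safety review. This is fair and lowers the weight of the point, but none of these routes starts from the score.

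A reader might go further and infer that the wait-list withholds depression care. It does not: the wait-list delays an exercise program, and nothing in the documents bars outside treatment. A reader might also infer that outside treatment started during the wait would bias the Hypothesis 2 comparison. The documents support neither a size nor a direction for that. The items of the medication measure in C2.3 and the interviews mentioned in D.1.2 and D.1.5 cannot be seen, so it cannot be said that treatment use goes unrecorded.

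**Conclusion.** The point holds as a minor patient-safety improvement. As written, C2.1 attaches the list to score plus refusal, and so leaves out enrolees in both arms and willing but ineligible people with the same score. This is more than a missing detail, because the stated condition itself excludes them.

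The number of enrolees concerned is unknown, from 0 to 20 at full enrolment. A reader might take from the design that about half of the high scorers, or some definite number, will be waiting. No such count is supported, because the documents give no distribution of scores above 4.

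The conclusion rests on two assumptions: that C2.1 is followed as worded, and that the unseen consent form does not already give enrolees the list. If it does, what remains for enrolees is a cross-reference in C2.1, and the gap for willing but ineligible people may still be open. The point does not bear on the validity of the planned analyses.

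**What to change.** Amend C2.1 so that everyone scoring 10 or higher at screening receives the existing treatment-facility list, regardless of refusal, eligibility or later arm. If the consent form already does this for enrolees, say so in C2.1 and extend the rule to people who are willing but ineligible.

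The cost is one sentence in the protocol and an existing list handed to more people. Because the screen comes before randomisation, the list can be given under the same rule to future members of both arms. The downside is that it may slightly raise the use of outside treatment in either arm, which is acceptable for people above the plan's own referral threshold.
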